The estimated prevalence of LQTS is approximately 1/2,000 live births (3). Disease-causing mutations were found in 43% of the infants with a QTc > 470 ms, and 29% of those with a QTc between 461 and 470 ms; however, genetic screening was only performed in 14 of 28 (50%) infants in this latter QTc range. When this is added to the high probability that among the 196 non-genotyped infants with a QTc between 450 and 460 ms, there might be at least some LQTS mutation carriers, it is reasonable to assume that the prevalence of LQTS in

neonates may be higher than 1 in 2,000 (3). Finally, among patients with a definite clinical diagnosis of LQTS, approximately 20% are still genotype-negative. Thus, a LQTS prevalence of 1 in 2,000 in screened infants may still be a conservative estimate. With respectively 4 and 5.2 million live births per year in the United States and Europe (27 countries), the 1/2000 prevalence estimate predicts about 2,000 and 2,600 new cases of LQTS annually. Nationwide studies in Denmark and the Netherlands suggest that 50-60% of sudden unexpected deaths in children 1-18 years of age were due to inherited cardiac diseases (11).

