Available data (3) suggest when to perform neonatal screening and how to design a reasonable protocol. In the 3rd-4th week of life, the QT pattern has stabilized which is still in the timeframe prior to the most common window for SIDS vulnerability (i.e. 2-4 months of age). As errors in measurement are possible and developmental changes may still occur (12), it is recommended to act only on the basis of a second ECG which should be performed whenever the first ECG shows a QTc of 450-460 ms. If the second ECG has a QTc (Bazett's correction) exceeding 460 ms (1.3/1,000, Figure 1), LQTS genetic testing involving at least the 3 major LQTS susceptibility genes is performed. If the QTc is >470 ms (0.7/1000), or if a mutation is identified, β -blocker therapy is recommended. In the more common situation that the first QTc is between 450 and 460 ms (0.4/1000), it may be decided to obtain one or more follow-up ECGs over a short period of time to make an evaluation contingent on the outcome of multiple ECGs. In all cases, family history is considered as well as ECG assessment in first-degree relatives. In the prior study, >40% of the infants with a QTc >470 ms had a disease causing mutation, and >90% of the infants whose QTc remained prolonged at 1 year of life had a positive genetic test (3). See Figure 1 below for a graphical representation of this protocol.

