Even though screening in the neonatal period enables the identification of "at risk" infants prior to the peak incidence of SIDS (2-6 months), screening in the elementary schools has a strong rationale as well, especially when feasibility is concerned, as shown by the large program ongoing in Japan. The most recent report from the Kanazawa City Prefecture assessed the prevalence of genetically identifiable LQTS in a population of 7961 1st and 7th graders who underwent ECG screening and determined that at least 1 in 2653 subjects had an identifiable LQTS mutation (13). This is remarkably similar to the prevalence of LQTS found by Schwartz *et al.* in neonates (3), particularly considering that the data on SIDS (4) suggest that some LQTS neonates may not survive past 1 year of age. Approximately 12-15% of newly identified patients with LQTS have *de novo* mutations, while the rest are inherited paternally or maternally, which may be undiagnosed in other family members. Once the infant with LQTS is diagnosed, the family members can be screened phenotypically, and when a disease-causing mutation has been found in the proband, mutation-specific "cascade screening" (14,15) is performed in the family. The overall process has the potential to identify both neonates and older related individuals who are affected, and to importantly reassure those family members that test negative for the mutation, a multiple bonus that increases the benefits that accrue from this approach.

Significant questions have been raised regarding the effect of false positive findings as an unwanted cost of ECG screening for LQTS (16,17). It is important to understand that the threshold QTc used for diagnosis is the primary determinant of the test sensitivity and specificity. Raising the threshold QTc for screening diagnosis would increase the specificity and significantly reduce the number of false positives. The available data (3) point to a low expected false positive rate for those with a QTc >460 ms (<1/1,000, ~38/43,080 neonates in Figure 1), but to about 4.5/1000 for those with a QTc >450 ms. Thus, the false positive rate will be dependent on the QTc cut-off determined for follow-up.

[figure not shown]

Figure 1: LQTS diagnostic protocol at 3 to 4 weeks of life.

Cost Effectiveness and the Commercial Potential of LQTS Screening

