ECG diagnostics usually require a trained clinician to interpret the data in the context of the signs and symptoms of the patient. The tracings of the ECG provide information regarding heart rhythm, whether electrical impulses are conducting normally throughout the heart, or whether any part of the heart is contributing more or less than expected to the electrical activity. Modern ECG machines often include analysis software that interprets the acquired signals, but often manual over-reading of these conclusions is necessary. We will utilize the validated pediatric and adult Glasgow ECG interpretation algorithm in the proposed instrument, which has a demonstrated QTc reporting accuracy and is FDA-approved for diagnostic ECG applications. A primary care physician will screen patients using the proposed diagnostic instrument (the QTc Meter) at well child visits. The proposed specialized LQTS screening apparatus will cost less than \$50 to manufacture and will utilize 3 patient leads to categorize diagnostic likelihood of LQTS via the diagnostic algorithm into low (less than a 1 in 2000 chance) or high (~50% chance) risk, as indicated by signal averaged, and time domain analyzed ECG determination of the QTc. A dedicated simple-to-use machine will be fast and reliable in the primary care environment. Such a machine does not exist presently.

[figure not shown]
Study Design and Methods

Methods: *Describe, in detail, the research activities that will be conducted under this protocol:*

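### Do the Background's QTc screening rates and the roughly 50% high-risk figure have to be reconciled before this study can proceed?

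*Protocol*

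**What the plan says.** All the figures come from narrative sections of the protocol that summarise an earlier neonatal ECG cohort or describe the envisaged product.

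- **Background, paragraph on the screening protocol:** "In the more common situation that the first QTc is between 450 and 460 ms (0.4/1000". The same paragraph gives the rate of a QTc "exceeding 460 ms (1.3/1,000, Figure 1" and then "If the QTc is >470 ms (0.7/1000".
- **Background, paragraph on prevalence:** some carriers may exist "among the 196 non-genotyped infants with a QTc between 450 and 460 ms". Mutation yields are 43% above 470 ms and 29% at 461-470 ms, where 14 of 28 infants were genotyped. Prevalence is put at about 1 in 2,000, possibly a conservative figure, and about 20% of clinically definite cases are genotype-negative.
- **Background, paragraph on false positives:** above 460 ms the rate is "<1/1,000, ~38/43,080 neonates in Figure 1". The text continues "but to about 4.5/1000 for those with a QTc >450 ms" and concludes that "the false positive rate will be dependent on the QTc cut-off determined for follow-up".
- **Research Question and Aims:** the envisaged pathway uses 460 ms on two serial follow-on ECGs, with about 1 false positive in 1,000.
- **(b) Innovation:** the device will classify infants "into low (less than a 1 in 2000 chance) or high (~50% chance) risk".

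**The concern.** Two things look wrong.

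First, the 450-460 ms band is described as the more frequent finding, yet its rate is the lowest of the three in that paragraph: 0.4 per 1,000, against 1.3 above 460 ms and 0.7 above 470 ms. The count of 196 infants elsewhere in the Background points to a rate roughly ten times higher.

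Second, the 50% chance attached to a high-risk reading has no cutoff, test stage or prevalence beside it, and it does not equal any yield that the Background states.

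If these numbers fed the design, the stakes would be real. The share of flagged infants who are truly affected is the central quantity for a screening device, and it changes several-fold with the rate assumed just below 460 ms.

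**Working it through.** **Inputs (all from the protocol).** 196 infants at 450-460 ms; 28 infants at 461-470 ms; denominator 43,080 (another Background paragraph says more than 44,000); 0.7 per 1,000 above 470 ms; 1.3 per 1,000 above 460 ms (1.4 in the cost-effectiveness section); 38 false positives above 460 ms; about 4.5 false positives per 1,000 above 450 ms; yields 43% and 29%; prevalence 0.5 per 1,000.

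**Step 1. Does 0.4 per 1,000 reproduce?**
- Implied count: 0.0004 × 43,080 = 17 infants, against 196 stated.
- Rate from the count: 196 / 43,080 = 4.55 per 1,000 (196 / 44,000 = 4.45).
- Ratio: 4.55 / 0.4 = 11.4.
- From the false-positive paragraph alone: 4.5 - 38/43,080 × 1,000 = 4.5 - 0.88 = 3.6 per 1,000 in the band, and 3.6 / 0.4 = 9.

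It does not reproduce by any route.

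**Step 2. Do the neighbouring figures agree?**
- 28 / 43,080 = 0.65 per 1,000; 0.65 + 0.7 = 1.35, which fits the stated 1.3 and 1.4.
- Carriers: 0.0007 × 43,080 = 30.2 infants above 470 ms; 30.2 × 0.43 = 13.0; 28 × 0.29 = 8.1; total 21.1. That is about 1 in 2,040, which fits 1 in 2,000.

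So the 0.4 is a single outlier in an otherwise coherent set.

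**Step 3. What chance of disease do the stated figures give?** The share affected is prevalence / (prevalence + false-positive rate), or prevalence / positive rate, assuming that every case is flagged.

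| Cutoff | Calculation | Share affected |
|---|---|---|
| >450 ms | 0.5 / (0.5 + 4.5) | 10% |
| >450 ms, by counts | 21.1 / (30.2 + 28 + 196) | 8% |
| >460 ms | 0.5 / (0.5 + 1.0) | 33% |
| >460 ms | 0.5 / (0.5 + 0.88) | 36% |
| >460 ms | 0.5 / 1.3 | 38% |
| >470 ms | stated yield | 43% |

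Counting the 20% of cases that are genotype-negative gives 0.36 / 0.8 = 45% above 460 ms and 0.43 / 0.8 = 54% above 470 ms. With reconstructed counts (assuming that all infants above 470 ms were genotyped), 13/30 has an exact 95% interval of 25-63%, and 17/44 among those genotyped above 460 ms has 24-55%. Both intervals contain 50%.

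**Step 4. Does anything in the study use these numbers?** Enrolment is set at 500 controls and 500 children with LQTS, plus 50 healthy subjects for calibration, giving a target of 1,050. None of these is computed from a screening rate. Inclusion and exclusion depend on age, diagnosis, gestation, congenital heart disease and implanted devices, with no QTc cutoff. The Data Analysis section states no calculation that draws on these rates. The cost-effectiveness text on genetic testing uses 1.4 per 1,000 above 460 ms, not the disputed band.

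**The case for a change.** The strongest case for a correction is that the contradiction sits in the visible text and needs no outside source: the band said to be more frequent cannot be the rarest in its own paragraph. The wording refers to a first ECG, so 0.4 cannot easily be read as a second-ECG rate. The meter's own trigger value is not fixed. Anyone weighing a 450 ms trigger would get 0.4 + 1.3 = 1.7 infants flagged per 1,000 from one paragraph (0.5 / 1.7 = 29% affected) and 4.55 + 1.3 = 5.9 from the counts (8% affected). The repair would cost one number and a clause.

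The contradiction stands. The consequences do not carry as far:

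- The 460 ms cutoff for the follow-on ECGs is stated in Research Question and Aims, so the arithmetic at 450 ms tests a cutoff that the protocol does not propose. It also adds a first-ECG rate to one that the text attaches to a second ECG.
- The 4.5 per 1,000 is a cumulative false-positive rate above 450 ms. It is not a rate for the band, so its near-match with 196/43,080 is not independent confirmation.
- The 50% can be approached in several ways: a threshold above 470 ms (yields already rise from 29% to 43%), persistence of prolongation (a positive test in over 90% of infants still prolonged at one year), genotype-negative cases, or a prevalence above 1 in 2,000. Excluding genetically elusive LQTS from enrolment does not remove such cases from a future screened population. The figure lacks a stated basis, but that does not make it wrong.

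**Conclusion.** The rate of 0.4 per 1,000 for a first QTc of 450-460 ms is inconsistent with the rest of the Background by a factor of about 9 to 11. It is best regarded as a clerical slip. A misplaced decimal is possible, but that is an assumption, because Figure 1 is not shown and cannot be checked. The roughly 50% in (b) Innovation is an approximate, unsourced aim for a later product. The stated yields of 33-43% at the higher cutoffs lie somewhat below it without excluding it.

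No change to the plan follows. The numbers describe published data and a future use of the device. They determine no enrolment target, eligibility rule, endpoint or analysis in this protocol, and correcting them would not alter what is done to any child or what the study can conclude. The sponsor may tidy the rate when the Background is next edited. The conclusion would differ only if a later document took the 450-460 ms rate or the 50% figure as a design input or performance target; nothing in this protocol does so.

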Phase II Novel Low Cost QTc Meter for Long QT Syndrome Screening in Primary Care

NCT04441892

July 24, 2019

IRB Minimal Risk Protocol Template

General Study Information

Principal Investigator: [name] [name]

Study Title: Phase II Novel Low Cost QTc Meter for Long QT Syndrome Screening in Primary Care

Protocol version number and date: Version 4 7.24.2019

Research Question and Aims

Hypothesis: To specify, develop, and evaluate a diagnostic algorithm suitable for use in an inexpensive diagnostic instrument suitable for screening for LQTS in the primary care environment.

Aims, purpose, or objectives:

Blue Ox Health Corporation in collaboration with the Mayo Clinic, Minnesota Health Solutions, and the University of Rochester (New York), proposes to develop an inexpensive diagnostic instrument (the QTc Meter) specifically designed to support widespread screening for the QT interval in aiding of diagnosis of long QT syndrome (LQTS) in the primary care setting. Congenital LQTS satisfies several criteria that makes widespread screening worthwhile: LQTS is not rare (1 in 2,000 births), follow-on ECG diagnosis is feasible and ideally complemented by genetic testing, LQTS may cause up to 10% of sudden infant death syndrome (SIDS) and 15% of autopsy negative sudden unexplained death syndrome (SUDS) between ages 1 and 35, and highly effective treatments are available (1,2,3,4,5). Further, by stimulating cascade screening, diagnosis of affected infants may prompt identification of asymptomatic, but affected, and potentially at-risk family members.

The cost and complexity of existing diagnostic electrocardiography technologies make them incompatible with widespread screening for LQTS in the primary care setting. Existing FDA-approved single or multi-lead ECGs are not designed for fast, inexpensive, simplified QTc reporting. The proposed novel instrument will be purpose-built, with a validated QTc reporting automated ECG analysis program and simple low-cost display, for the specific task of QTc reporting in the primary care environment. We believe the proposed reusable battery powered handheld QTc Meter can be manufactured for under \$50.

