Infant screening using the proposed instrument will be cost-effective using conventional criteria, and with a QTc cutoff of 460 ms in two serial follow-on ECGs triggered by an abnormal value on the QTc meter, the number of false positives is estimated to be low (~1 in 1,000) (2). We envision the parents of newborn children being informed about LQTS, a treatable disease that can cause life-threatening arrhythmias in infants, children, and young adults occurring in 1 in 2,000 births, and informed that early diagnosis is achievable by adequate screening and any required follow-on diagnostics.

The objective of the proposed project is to further develop and evaluate a diagnostic algorithm suitable for use in an inexpensive diagnostic instrument suitable for screening for LQTS in the primary care environment. We plan to develop novel technology enabling the screening of newborns for the presence of abnormal QT/QTc interval prolongation. During this phase II study we propose to test a newly built prototype (upgraded from the

prototype used in phase I), validate the new algorithm in a cohort of 1,000 newborns/children and demonstrating the ability of the QTc meter to screen newborns for LQTS and help clinicians to improve patient management and save lives. The phase II project will finalize the algorithm design from phase I and fully validate its performance in a study informed by the phase I pilot evaluation.

Aim 1: Assemble a prototype system to enable the recording of the surface ECGs with the technical specification fitting the standard technical requirements for FDA-approved clinical ECG devices. Use the upgraded prototype developed base off results from the Phase I study to record ECGs in a cohort of 1,000 newborns/children to form a learning dataset for the Aim 2. This includes 500 control subjects and 500 with LQTS.

Aim 2: Evaluation of the usability and performances of the QTc Meter in a validation study conducted at the Mayo Clinic's LQTS Clinic

Objective:

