An updated prototype QT meter has been developed following the results obtained in phase I of the study. This new device, with its new enhancements, will be able to be paired with an associated app via Bluetooth and connected with a database in the cloud. Because this device is now Bluetooth enabled it will no longer need to be directly connected to the ECG machine. Phase II of the study will involve acquiring ECG data in a cohort of up to 1,000 newborns and infants (500 controls (non-LQTS) and 500 LQTS newborns and infants) that are being seen in the Gonda SL ECG Lab (or Baldwin Building) and enrolled during their appointment for a clinically indicated 12-lead ECG. A second arm of Phase II of this study will include approaching 50 healthy subjects at the Baldwin Building to seek interest in participation which will consist of (1) 30 second device recording to help further calibrate and test the device for optimal enhancement. These 50 subjects will not be required to have a clinical or research 12-lead ECG as we will be simply testing the efficiency and accuracy of the device. LQTS will be studied in order to assess the ability of the LQTS screener to accurately detect a patient with established QT prolongation in the context of distinct and varied T wave morphologies. The advanced prototype will be placed in the same manner as the device used in Phase I of the study by being lightly placed on the child as pictured below. Similarly, we will use ultrasound gel to obtain a better reading, if applicable. Once completed, a photograph of the torso of the child will be taken from the same views as before (one aerial view and one side view) with neither the head nor the face in the picture. Coded ECG-tracings will be transmitted to the app and shared with Blue Ox Health Corporation and Minnesota Health Solutions as done previously in phase I. Additionally, coded tracings and data from the 12-lead ECG will be shared with Blue Ox Health Corporation and Minnesota Health Solutions to aid in comparison to device tracings and optimization of the algorithm. The 12-lead ECG will be obtained from the subject's medical record and coded before being shared with collaborators. Study coordinators will also review the patient's medical record to determine whether they have been diagnosed with a genetic disease.

Phase I Prototype

Phase II Prototype

Potential risks to the patient:

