Potential risks of the protocol include skin reactions to the ECG electrodes or ultrasound gel. This device currently does not have an indicated use for patients with cardiac devices therefore to avoid this unknown risk we will not be enrolling any patients with a pacemaker/ICD.

Resources: *Describe the available resources to conduct the research (personnel, time, facilities, mentor commitment, etc.):*

Screening will utilize the study coordinator and nurse of Mayo Clinic's LQTS Clinic who will review the schedule of returning, established LQTS children who would meet the study's eligibility criteria. If eligible, the infant/child's parents would be contacted at their annual clinical evaluation and informed of the study. If the parent agrees, consent will be obtained prior to the child's clinical 12-lead ECG in the Gonda SL ECG Lab. The study procedure, i.e. the application of the QTc Meter, will be initiated following consent.

(1a) This is a multisite study involving Mayo Clinic and non Mayo Clinic sites. *When checked, describe in detail the research procedures or activities that will be conducted by Mayo Clinic study staff.*

(1b) Mayo Clinic study staff will be engaged in research activity at a non Mayo Clinic site. *When checked, provide a detailed description of the activity that will be conducted by Mayo Clinic study staff.*

Subject Information

Target accrual is the proposed total number of subjects to be included in this study at Mayo Clinic. A "Subject" may include medical records, images, or specimens generated at Mayo Clinic and/or received from external sources.

Target accrual: 1,050 subjects

Subject population (children, adults, groups):

Newborns/Children ages 5 and under

Inclusion Criteria:

1. Infants/Children (Day 0-Age 5)
2. Long QT Syndrome (LQTS)
3. Newborns without LQTS (Controls)
4. Parental willingness to provide informed consent and follow the study protocol

Exclusion Criteria:

5. Children > 5 years old
6. Those with genetically elusive LQTS
7. Infants with congenital heart disease
8. Infants born <32 weeks EGA
9. Patients with a cardiac device implant (pacemaker/ICD)

Research Activity

Check all that apply and complete the appropriate sections as instructed.

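### Does recruiting the LQTS group by diagnosis, with no QTc criterion, conflict with using it to test detection of established QT prolongation?

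*Protocol*

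**What the plan says.** Research Question and Aims presents a device for "screening for the QT interval in aiding of diagnosis of long QT syndrome" and technology "enabling the screening of newborns for the presence of abnormal QT/QTc interval prolongation". For the cohort of 1,000 it states the goal as "demonstrating the ability of the QTc meter to screen newborns for LQTS". The Innovation section links the two: the device sorts children into low or high likelihood of LQTS, "as indicated by signal averaged, and time domain analyzed ECG determination of the QTc".

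Study Design and Methods sets the cohort at "500 controls (non-LQTS) and 500 LQTS newborns and infants", all enrolled at an appointment for a clinically indicated 12-lead ECG. It gives the reason for studying LQTS as assessing the screener's ability "to accurately detect a patient with established QT prolongation in the context of distinct and varied T wave morphologies". Coded 12-lead data go to the collaborators for comparison with the device tracings and for optimizing the algorithm. Coordinators also check the medical record for a diagnosed genetic disease.

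Under Resources, the clinic staff "review the schedule of returning, established LQTS children". The inclusion list names LQTS and newborns without LQTS, and the exclusion list removes "Those with genetically elusive LQTS". Neither list contains a QTc value.

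**The concern.** QT prolongation is an ECG finding; LQTS is a disease. The sentence in Study Design and Methods gives the finding as the thing to be detected, while the aims and the eligibility criteria refer to the disease. Nothing in selection guarantees that a child with an LQTS diagnosis has a prolonged QTc on the study day. The Background itself thinks it likely that some mutation carriers lie among infants with a QTc of 450 to 460 ms, which is not above the 460 ms cut-off used elsewhere in the protocol.

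Take an LQTS child whose 12-lead QTc is not prolonged at the visit and whose meter reading agrees with it. If the question is whether the meter reads QTc correctly, the meter is right. If the question is whether a QTc screen finds LQTS, the screen has missed a case. If LQTS status were used as the reference for QT prolongation, a correct meter would be charged with errors that belong to the disease definition. If the choice were left until results were known, the more favourable version could be reported.

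**Working it through.** The protocol gives no power statement or effect size on this point, so there is no planned figure to reproduce. The check is a comparison of texts, followed by a scale calculation on assumed values.

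**Comparison of texts**

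1. *Target.* The aims, the Innovation section and the Methods sentence describe one chain: measure QTc in order to screen for LQTS. The Methods sentence itself calls the device an LQTS screener.
2. *Meaning of the phrase.* The Background twice describes LQTS as characterized by QT prolongation. Read with recruitment of established LQTS children, the Methods sentence explains why these children are useful: they supply prolonged QT with varied T-wave shapes.
3. *Scoring.* No section says that LQTS children count as QT-positive, and the Methods sentence names neither a reference nor a scoring rule.
4. *Comparator.* The only comparison described for the device tracings is with the paired 12-lead ECG, which suits the question of QTc accuracy. LQTS status is also recorded, which suits the question of screening.
5. *Evidence of divergence.* The 450 to 460 ms remark concerns non-genotyped infants from a population screened at 3 to 4 weeks of life, and the Background treats that band as calling for a repeat ECG. It shows that diagnosis and a QTc above the cut-off need not coincide. It does not say how often they differ among returning clinic patients up to age 5. The Background's description of cascade screening in families says nothing about carriers' QTc.

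**Scale**

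Inputs: n = 500 LQTS children (protocol); sensitivity 0.95 for truly prolonged QTc (assumed); c = share of LQTS children whose 12-lead QTc is not prolonged at the visit (unknown, possibly zero).

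- With LQTS status as the reference and no false alarms, apparent sensitivity = 0.95 × (1 − c).
- 95% half-width = 1.96 × √(0.95 × 0.05 / n). At n = 500 this is 0.0191, or 1.9 points.
- The shift 0.95 × c equals that half-width when c = 0.0191 / 0.95 = 0.0201, and 0.0201 × 500 = 10.1 children.
- Check: 10 of 500 gives c = 0.02, and 0.95 × 0.98 = 0.931, a loss of 1.9 points.
- Analysing only the children with a prolonged 12-lead QTc costs little precision: the half-width is 0.0201 at n = 450 and 0.0247 at n = 300.

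The false-positive rates in the Background are not used here for controls. They come from neonatal screening, whereas these controls are enrolled at a clinically indicated ECG in a study admitting children up to age 5.

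**The case for a change.** The strongest case for a change is that purpose and eligibility both stand in this protocol, so a mismatch between them cannot be dismissed as something left to an analysis plan. A small share is enough to matter: about 2% of the LQTS group on the assumption above. The Background says that the QTc threshold is the main determinant of sensitivity and specificity. The remedy would be a sentence of wording, with no new data.

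Part of this stands. The Methods sentence is imprecise, the protocol does not treat LQTS and a QTc above its cut-off as identical, and an LQTS child without prolongation would count differently under the two questions.

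The rest does not carry. The harm needs a further step, scoring every LQTS child as QT-positive, which the protocol nowhere takes. The 2% is a break-even point on an assumed sensitivity; it is not evidence that such children occur at that rate. Nor is the eligibility defective. Selection by diagnosis is right for a study of LQTS screening, and admitting only children with prolonged QTc would inflate the apparent sensitivity for LQTS. What is left is a request to name the reference for each result and to fix a cut-off beforehand. Those are analysis specifications, and an analysis plan that is not shown may hold them.

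**Conclusion.** No change to the plan is needed. The sentence uses an ECG finding as shorthand for the disease, within a protocol whose target is otherwise consistent. The 12-lead QTc and LQTS status are both collected in the 1,000 subjects. An analyst can compare meter QTc with 12-lead QTc, and separately report how well the meter distinguishes LQTS from non-LQTS, without altering eligibility or procedures.

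The size of any effect cannot be stated, because the share c is not in the protocol and may be zero. The only scale available is the break-even of about 10 children in 500, which rests on the assumed 95% sensitivity and on a scoring rule the protocol does not contain. The conclusion would differ if the analysis did use LQTS diagnosis as the reference for QT prolongation; nothing in the protocol says that it will.
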